## 15.4 Efficacy evaluation

Descriptive statistics will be calculated for all endpoints before, during, and after treatment. Changes before and 6 months after treatment in biochemical endpoints will be tested with two-sided paired t-tests. This analysis will be supplemented with single group repeated measures ANOVA to test for effects over time since there are 3 measures on treatment. Many secondary endpoints are counts (e.g. frequency of refills of opioids, number of hospitalizations). Depending on the distributions of these outcomes, we will either: 1) dichotomize and compare with McNemar's test; 2) treat as ordinal and compare with a Cochran-Mantel-Hazensel type test; or 3) treat as continuous and conduct either paired t-test or Wilcoxon signed rank tests. Since the pain measure will depend on age, we will only statistically analyze when there are at least 6 participants using a single-group repeated measures ANOVA model. Otherwise, only graphical descriptions will be used.

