### 4.2 Secondary Aims

- 4.21 To assess the effect of imatinib on the frequency of vaso-occlusive pain events in patients with sickle cell disease
- 4.22 To assess the effect of imatinib on the amount of opioid use, frequency of acute chest syndrome, and number of hospitalizations
- 4.23 To assess the tolerability and toxicity of imatinib in patients with sickle cell disease

The clinical outcome will be a secondary aim due to the relatively short duration of the study; we expect to see a reduction in the frequency of vaso-occlusive crises, utilization of opioids, and number of hospitalizations and possibly in the incidence of acute chest syndrome and other SCA-associated complications.

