## 5.0 INVESTIGATIONAL PLAN

### 5.1 Study Design

This will be an open label nonrandomized pilot study to determine the effect of imatinib on band 3 phosphorylation, microparticle release from sickle RBCs, and percent irreversibly sickled cells obtained from adolescent and young adult patients with Hemoglobin SS Disease or S-Beta 0 Thalassemia before, during, and after 6 months of treatment with imatinib. We will also look at clinical outcomes during treatment (pain) and before treatment. Clinical outcomes before treatment will be collected via retrospective chart review.

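### The test for the secondary count endpoints is chosen after their distributions are seen, with no rule or cut-point, and one permitted option (dichotomise, then McNemar) does not fit the frequency aim and can lose half or more of the power

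*Combined protocol and SAP*

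**What the plan says.** Section 4.2 sets the clinical aim as "To assess the effect of imatinib on the frequency of vaso-occlusive pain events", with opioid use, acute chest syndrome and hospitalizations beside it. It explains the ranking: "The clinical outcome will be a secondary aim due to the relatively short duration of the study". Section 5.1 describes the design: "This will be an open label nonrandomized pilot study". It adds that "Clinical outcomes before treatment will be collected via retrospective chart review", without giving the length of the look-back.

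Section 15.4 recognises that many of these endpoints are counts and continues: "Depending on the distributions of these outcomes, we will either: 1) dichotomize and compare with" McNemar's test, or take them as ordinal with a CMH-type test, or "treat as continuous and conduct either paired t-test or Wilcoxon signed rank tests". That makes four tests. The section does not say which features of a distribution lead to which test, where a count would be cut, whether McNemar is exact or asymptotic, when the decision is taken, or how unequal follow-up is handled. The biochemical endpoints, by contrast, have a fixed test: a two-sided paired t-test.

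**The concern.** Choosing a test from the shape of the data can be harmless when that shape carries no information about the effect, as with pooled data in a blinded trial. Here there is one open-label arm, and the before and on-treatment distributions are the comparison itself. Section 18.1 also has the investigators meeting monthly over the data and the responses seen. Whoever picks the test or the cut-point can therefore already see which way the result goes.

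The McNemar option raises a separate difficulty. Section 5.2.1 admits only patients with at least two pain episodes in the prior year. Scored as any versus none, a fall from four events to two counts as no change. A dichotomy also has no natural way to allow for patients who stop early and have less follow-up. At stake are a real fall in events being missed, and a p-value that a reader cannot take at face value.

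**Working it through.** **The plan's only power figure.** Section 15.1 gives mean 140,000, SD 75,000, a fall of 70,000, correlation 0.5, n = 20 and two-sided alpha 0.05/5 = 0.01.
- SD of the difference = √(2 × 75,000² × (1 − 0.5)) = 75,000.
- Noncentrality = (70,000/75,000) × √20 = 4.17, with 19 degrees of freedom.
- Power = 88.98%, which reproduces the stated 89%.

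This concerns microparticles. No rate, effect size, alpha or power is given for any count endpoint, so the inputs below are assumptions apart from n = 20, the 6-month treatment period and the entry rule.

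**Simulation without the entry rule.** Each patient has a multiplier g from a gamma distribution with mean 1 and shape k (or g = 1 for pure Poisson). Before-count ~ Poisson(μg) and on-treatment count ~ Poisson(μ·RR·g), with equal 6-month periods, RR = 0.5 for power and 1 for type I error, two-sided 5%. With b and c the two kinds of discordant pair, exact McNemar p = min(1, 2·P[Bin(b+c, ½) ≤ min(b, c)]). The paired t, Wilcoxon and CMH mean-score tests use the within-patient difference.

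With k = 1 or 2 and μ = 1 to 3 (4,000 trials per setting), power is 10-17% for exact McNemar any versus none and 35-82% for paired t or Wilcoxon. At μ = 2, k = 1: McNemar any versus none 0.119, McNemar cut at more than one event 0.175, CMH-type 0.594, paired t 0.609, Wilcoxon 0.619.

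A second set (6,000 trials per setting) gives power in % as k = 2 / pure Poisson:

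| Mean per 6 months | Exact McNemar, any/none | Uncorrected, any/none | Exact, best cut | Uncorrected, best cut | CMH | Paired t | Wilcoxon |
|---|---|---|---|---|---|---|---|
| 1 | 16.5 / 20.5 | 25.2 / 28.4 | 16.5 / 20.5 | 26.3 / 28.4 | 37.6 / 39.6 | 38.9 / 40.6 | 38.8 / 39.8 |
| 2 | 17.7 / 24.4 | 28.1 / 36.2 | 28.1 / 41.6 | 41.4 / 52.0 | 63.9 / 68.9 | 65.4 / 70.1 | 64.8 / 68.9 |
| 3 | 12.5 / 13.2 | 26.6 / 33.8 | 35.8 / 58.4 | 53.2 / 68.2 | 80.3 / 84.9 | 81.7 / 85.8 | 80.7 / 84.5 |

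Exact any/none therefore keeps 43-52% of Wilcoxon's power at mean 1, 27-35% at mean 2 and 15-16% at mean 3. The best cut is known only with hindsight. With no variation between patients, exact any/none reaches 24%, somewhat above the 10-17% range.

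**Simulation with the entry rule, pain events only.** Patients were required to have at least two events in the 12 months before treatment. The before-window was taken as the last 6 of those months (assumed), with k = 1 or 2 and a source mean of 1 to 3. Under a halving, exact McNemar any/none has about 21-67% and Wilcoxon about 87-95%. Across those ranges McNemar keeps no less than 21/95 = 22% and no more than 67/87 = 77%. Part of both figures is regression to the mean: with no drug effect, Wilcoxon itself rejects in about 5-18% of trials.

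**Type I error from choosing, no entry rule.** Taking the smallest p over the listed tests rejects in about 5-6% of null trials with exact McNemar fixed at any/none, and about 6-8% with exact McNemar and a free cut-point from 1 to 6. With uncorrected McNemar and a free cut-point it is 9-22%. One test fixed in advance (Wilcoxon or paired t) stays at about 4-5%.

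**Why the look-back matters.** If the before-window were the whole qualifying year, every patient would score "any" before treatment and discordant pairs could go only one way. Six event-free patients on treatment would then give p = 2 × 0.5⁶ = 0.031 whether or not the drug works.

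**The case against.** These are secondary endpoints of a pilot, with no alpha or power claim attached, and the primary analysis is fixed. Descriptive statistics are promised for every endpoint whichever test is used. The choice is said to depend on distributions, not on p-values, so a smallest-p search is a worst case. All of this stands, and it limits the point to a minor one.

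Three stronger readings are tempting, and the documents do not support them.
- A reader might infer that dichotomising is the default because it comes first. Section 15.4 ranks nothing.
- A reader might infer that the plan gives up most of its power on these endpoints. That would need option 1 to be chosen, usually with exact McNemar and an any/none split. About half the power is kept at mean 1, a better cut-point or uncorrected McNemar keeps more, and the entry rule raises McNemar's power for pain events. No event rates are given, so no single loss can be fixed.
- A reader might infer that the 5% level is badly broken. The inflation is modest unless uncorrected McNemar is combined with a free cut-point. The plan does not exclude that combination, but it does not propose it either.

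The entry rule concerns pain episodes only. It does not show that hospitalizations or acute chest syndrome recur often; where events are few, every test has little power. There is no power case against the CMH-type test, which performs like the t and Wilcoxon tests; the case is only that one test should be named.

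**Conclusion.** The point holds in a limited form and is minor. Both test and cut-point are left to the observed data with no rule, in a design where those data reveal the effect. One permitted option suits the frequency aim poorly and, under the assumed rates, can lose half or more of the power. That size rests on an assumed halving, 1 to 3 events per 6 months, equal 6-month windows and 20 complete pairs. It shrinks with a well-placed cut-point, uncorrected McNemar, or low event rates among patients meeting the entry rule. Fixing the test does not by itself restore a 5% level for pain events, because patients are selected on a high prior-year count and regression to the mean affects every before/after test. The primary endpoints are untouched.

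**What to change.** In Section 15.4:
- Delete the dichotomise/McNemar option and the choice by distribution.
- Name one test for all count endpoints, for example Wilcoxon signed-rank on the within-patient difference in events per person-month.
- State a fixed pre-treatment look-back window for the chart review.
- Report a rate ratio with 95% CI from one named model with a log follow-up offset, for example Poisson with robust errors clustered by patient.
- Set in advance a total-event threshold below which only counts are reported; acute chest syndrome may well fall there.
- Say that selection on at least two prior-year pain events causes regression to the mean, which no choice of test removes.

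The cost is wording only. The downside is less flexibility for unusual data. Two smaller costs should be accepted openly: the Wilcoxon p-value and the model interval can disagree, so the text should say which carries the inference; and a per-person-month difference gives a short, noisy period from an early dropout the same footing as a full six months.

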## 16.0 INCLUSION OF CHILDREN, WOMEN, AND MINORITIES

The study is open to all participants regardless of gender or ethnicity. Efforts will be made to extend the accrual to a representative population. If differences in outcome that correlate to gender, racial, or ethnic identity that are outside of the expected distribution for this patient population are noted, accrual may be expanded or additional studies may be performed to investigate those difference more fully.

## 17.0 CORRELATIVE STUDIES (Please see Lab Manual)

## 18.0 DATA MANAGEMENT AND DATA SAFETY MONITORING

### 18.1 Monitoring and Reporting Guidelines

Investigators will conduct continuous review of data and patient safety. As accrual warrants, review meetings will take place monthly and will include principal investigators [name], MS; [name], [name], PhD, study coordinators and clinical research nurses. Monthly meetings will include review of data, the number of patients, significant toxicities as described in the protocol, and responses observed.

### 18.21. Early Study Closure

At any time during the conduct of the trial, if it is the opinion of the investigators that the risks (or benefits) to the subject warrant early closure of the study, the Compliance Officer must be notified within 1 business day via email, and the IRB must be notified within 5 business days. Alternatively, the investigators may initiate suspension or early closure of the study based on their monthly reviews.

### 18.3 Oversight of Study Progress

Data collection and data management for this study will be conducted with the support of the Center for Cancer and Blood Disorders Clinical Research Office and the Data Management Core at Indiana University School of Medicine. This team will be responsible for assisting the PI in assuring protocol compliance as well as reviewing, transcribing and tracking of all clinical and safety related data.

### **18.31. Continuing Review**

All Continuing Reviews will be reviewed annually or as dictated by the Institutional Review Board.

### **18.4 Study Data Management**

Primary data will be collected from treatment or test results included in the subject's medical record or source documentation given by the subject (i.e., patient diary). Patients will be registered in OnCore. Data will be entered on the Case Report Forms (CRFs) developed for this study stored electronically in REDCap. This database will be backed up automatically every week. Quality assurance steps will include: 1) built-in range checks; 2) testing of the database by the study team prior to moving to production mode; and 3) review and verification of all by the principal investigator and the research manager. Specific data questions will be given to the appropriate personnel who will then investigate and resolve the questions with the help of the investigator as necessary. Additionally, the following quality control methods will be used: 1) single entry of data with random checks of accuracy; and 2) extraction and cleaning of data that will be used for analysis every 6 months.

Data will be recorded on the CRFs and will be kept confidential with only the principal investigator, co-investigators, statisticians, IRB and the research personnel having access to individually identifiable data. The CRFs will be locked in a cabinet in a secure area with limited access to the building.

Data from this study will be retained for a minimum of 7 years for health data per Indiana State law. Following this period, paper will be shredded and permanently deleted from any computers.

Identifiable data will be shared only between research team members approved on the "Investigator List" in any of the following ways: encrypted email, US postal service or trackable courier services (i.e. FedEX), fax in a secured area, shared drive with password protection, personal delivery by authorized research personnel and/or private telephone conversations to authorized personnel.

## **19.0 PROCEDURES AND INSTRUCTIONS**

### **19.1 Administrative Procedures**

#### **19.1.1 Changes to the Protocol**

Any change or addition to this protocol requires a written protocol amendment that must be approved by all the principal investigators before implementation. Amendments significantly affecting the safety of subjects, the scope of the investigation or the scientific quality of the study, require additional approval by the IRB.

Amendments affecting only administrative aspects of the study do not require formal protocol amendments or IRB approval but the IRB of each center must be kept informed of such administrative changes.

### **19.2 Ethics and Good Clinical Practice**

This study must be carried out in compliance with the protocol and Good Clinical Practice, as described in:

- 21.21. ICH Harmonized Tripartite Guidelines for Good Clinical Practice 1996.
- 21.22. Directive 91/507/EEC, The Rules Governing Medicinal Products in the European Community.
- 21.23. US 21 Code of Federal Regulations dealing with clinical studies (including parts 50 and 56 concerning informed consent and IRB regulations).
- 21.24. Declaration of Helsinki, concerning medical research in humans (Recommendations Guiding Physicians in Biomedical Research Involving Human Subjects, Helsinki 1964, amended Tokyo 1975, Venice 1983, Hong Kong 1989, Somerset West 1996).

The investigator agrees, when signing the protocol, to adhere to the instructions and procedures described in it and thereby to adhere to the principles of Good Clinical Practice that it conforms to.

### **19.3 Institutional Review Board/Independent Ethics Committee**

Before implementing this study, the protocol, the proposed informed consent form and other information to subjects, must be reviewed by a properly constituted Institutional Review Board/Independent Ethics Committee (IRB/IEC/REB).

### **19.4 Informed Consent**

The investigator must explain to each subject (or legally authorized representative) the nature of the study, its purpose, the procedures involved, the expected duration, the potential risks and benefits involved and any discomfort it may entail. Each subject must be informed that participation in the study is voluntary and that he/she may withdraw from the study at any time and that withdrawal of consent will not affect his/her subsequent medical treatment or relationship with the treating physician.

This informed consent should be given by means of a standard written statement, written in non-technical language. The subject should read and consider the statement before signing and dating it, and should be given a copy of the signed document. If the subject cannot read or sign the documents, oral presentation may be made or signature given by the subject's legally appointed representative, if witnessed by a person not involved in the study, mentioning that the patient could not read or sign the documents. No patient can enter the study before his/her informed consent has been obtained.

## APPENDIX A: IMATINIB TABLETS DOSING GUIDELINES

### Imatinib 340mg/m^2/day

Body Surface Area (m  )	Total Daily Dose (Rounded to Nearest 50 mg)	Recommended Administration
≤ 0.36	100 mg	1 x 100 mg tablet once daily
0.37 – 0.51	150 mg	1 ½ x 100 mg tablets once daily
0.52 – 0.66	200 mg	2 x 100 mg tablets once daily
0.67 – 0.81	250 mg	2 ½ x 100 mg tablets once daily
0.82 – 0.95	300 mg	3 x 100 mg tablets once daily
0.96 – 1.10	350 mg	3 ½ x 100 mg tablets once daily
1.11 – 1.25	400 mg	4 x 100 mg tablets once daily
1.26 – 1.39	450 mg	4 ½ x 100 mg tablets once daily
1.4 – 1.54	500 mg	5 x 100 mg tablets once daily
1.55 – 1.69	550 mg	5 ½ x 100 mg tablets once daily
≥1.70	600 mg	6 x 100 mg tablets once daily

### Imatinib 260mg/m^2/day

Body Surface Area (m  )	Total Daily Dose (Rounded to Nearest 50mg)	Recommended Administration
≤ 0.29	50 mg	½ x 100mg tablet once daily
0.3 – 0.48	100 mg	1 x 100mg tablet once daily
0.49 – 0.67	150 mg	1 ½ x 100mg tablet once daily
0.68 – 0.86	200 mg	2 x 100mg tablet once daily
0.87 – 1.05	250 mg	2 ½ x 100mg tablet once daily
1.06 – 1.24	300 mg	3 x 100mg tablet once daily
1.25 – 1.44	350 mg	3 ½ x 100mg tablet once daily
1.45 – 1.63	400 mg	4 x 100mg tablet once daily
1.64 – 1.82	450 mg	4 ½ x 100mg tablet once daily
1.83 – 2.01	500 mg	5 x 100mg tablet once daily
≥ 2.02	550 mg	5 ½ x 100mg tablet once daily

### Imatinib 200mg/m^2/day

Body Surface Area (m  )	Total Daily Dose (Rounded to Nearest 50mg)	Recommended Administration
≤ 0.37	50 mg	½ x 100mg tablet once daily
0.38 – 0.62	100 mg	1 x 100mg tablet once daily
0.63 – 0.87	150 mg	1 ½ x 100mg tablet once daily
0.88 – 1.12	200 mg	2 x 100mg tablet once daily
1.13 – 1.37	250 mg	2 ½ x 100mg tablet once daily
1.38 – 1.62	300 mg	3 x 100mg tablet once daily
1.63 – 1.87	350 mg	3 ½ x 100mg tablet once daily
1.88 – 2.12	400 mg	4 x 100mg tablet once daily
2.13 – 2.37	450 mg	4 ½ x 100mg tablet once daily
≥ 2.38	500 mg	5 x 100mg tablet once daily

## APPENDIX B: Drugs known to be metabolized by CYP450 isoenzymes 2D6 and 3A4

CYP2D6	
Substrates	
Amitriptyline (hydroxylation)	Methamphetamine
Amphetamine	Metoclopramide
Betaxolol	Metoprolol
Bisoprolol	Mexitetine
Brofaromine	Mianserin
Buturolol	Mirtazapine (hydroxylation)
Bupropion	Molindone
Captopril	Nortriptyline (hydroxylation)
Carvedilol	Olanzapine (minor, hydroxymethylation)
Cevimeline	Ondansetron
Chlorpheniramine	Orphenadrine
Chlorpromazine	Oxycodone
Cinnarizine	Papaverine
Clomipramine (hydroxylation)	Paroxetine (minor pathway)
Clozapine (minor pathway)	Penbutolol
Codeine (hydroxylation, o-demethylation)	Pentazocine
Cyclobenzaprine (hydroxylation)	Perhexiline
Cyclophosphamide	Perphenazine
Debrisoquin	Phenformin
Delavirdine	Pindolol
Desipramine	Promethazine
Dexfenfluramine	Propafenone
Dextromethorphan (o-demethylation)	Propranolol
Dihydrocodeine	Quetiapine
Diphenhydramine	Remoxipride
Dolasetron	Risperidone
Donepezil	Ritonavir (minor)
Doxepin	Ropivacaine
Encainide	Selegiline
Fenfluramine	Sertindole
Flecainide	Sertratine (minor pathway)
Fluoxetine (minor pathway)	Sparteine
Fluphenazine	Tamoxifen
Halofantrine	Thioridazine
Haloperidol (minor pathway)	Tiagabine
Hydrocodone	Timolol
Hydrocortisone	Tolterodine
Hydroxyamphetamine	Tramadol
Imipramine (hydroxylation)	Trazodone
Labetalol	Trimipramine
Loratadine	Tropisetron
Maprotiline	Venlafaxine (o-desmethylation)
m-Chlorophenylpiperazine (m-CPP)	Yohimbine
Meperidine	
Methadone	
Inhibitors	
Amiodarone	Methadone

Celecoxib	Mibepradil
Chloroquine	Moclobemide
Chlorpromazine	Nortriptyline
Cimelidine	Paroxetine
Citalopram	Perphenazine
Clomipramine	Propafenone
Codeine	Quinacrine
Delavirdine	Quinidine
Desipramine	Ranitidine
Dextropropoxyphene	Risperidone (weak)
Diltiazem	Ritonavir
Doxorubicin	Sertindole
Entacapone (high dose)	Sertraline (weak)
Fluoxetine	Thioridazine
Fluphenazine	Vaiprolc acid
Fluvoxamine	Venlafaxine (weak)
Haloperidol	Vinblastine
Labetalol	Vincristine
Lobeline	Vinorelbine
Lomustine	Yohimbine

CYP3A4	Substrates	
	Acetaminophen Alfentanil Alosetron Alprazolam Amiodarone Amitriptyline (minor) Amlodipine Anastrozole Androsterone Antipyrine Astemizole Atorvastatin Benzphetamine Bepridil Bexarotene Bromazepam Bromocriptine Budesonide Bupropion (minor) Buspirone Busulfan Caffeine Cannabinoids Carbamazepine Cevimeline Cerivastatin Digitoxin	Chlorpromazine Cimetidine Cisapride Citalopram Clarithromycin Clindamycin Clomipramine Clonazepam Clozapine Cocaine Codeine (demethylation) Cortisol Cortisone Cyclobenzaprine (demethylation) Cyclophosphamide Cyclosporine Dapsone Dehydroepiandrosterone Delavirdine Desmethyl Diazepam Dexamethasone Dextromethorphan (minor, N-demethylation) Diazepam (minor; hydroxylation, N-demethylation) Nefazodone Nelfinavir Nevirapine Nicardipine

Diltiazem	Nifedipine
Disopyramide	Niludipine
Docetaxel	Nimodipine
Dolasetron	Nisoldipine
Donepezil	Nitrendipine
Doxorubicin	Omeprazole (sulfonation)
Doxycycline	Ondansetron
Dronabinol	Oral contraceptives
Enalapril	Orphenadrine
Erythromycin	Paclitaxel
Estradiol	Pantoprazole
Ethynodiol dihydrogesterone	Pimozide
Ethosuximide	Pioglitazone
Etoposide	Pravastatin
Exemestene	Prednisone
Dofetilide (minor)	Progesterone
Felodipine	Proguanil
Fentanyl	Propafenone
Fexofenadine	Quercetin
Finasteride	Quetiapine
Fluoxetine	Quinidine
Flutamide	Quinine
Glyburide	Repaglinide
Granisetron	Retinoic acid
Halofantrine	Rifampin
Hydrocortisone	Risperidone
Hydroxyarginine	Ritonavir
Ifosfamide	Salmeterol
Imipramine	Saquinavir
Indinavir	Sertindole
Isradipine	Sertraline
Itraconazole	Sibutramine
Ketoconazole	Sildenafil citrate
Lansoprazole (minor)	Simvastatin
Letrozole	Sirolimus
Levobupivacaine	Sufentanil
Lidocaine	Tacrolimus
Loratadine	Tamoxifen
Losartan	Temazepam
Lovastatin	Teniposide
Methadone	Terfenadine
Mibepridil	Testosterone
Miconazole	Tetrahydrocannabinol
Midazolam	Theophylline
Mifepristone	Tiagabine
Mirtazapine (N-demethylation)	Tolterodine
Montelukast	Vincristine
Navelbine	Warfarin (R-warfarin)
Toremifene	Yohimbine
Trazodone	Zaleplon (minor pathway)
Tretinoin	Zatoestron

Triazolam Troglitazone Troleandomycin Venlafaxine (N-demethylation) Verapamil Vinblastine	Zileuton Ziprasidone Zolpidem Zonisamide
Inducers	
Carbamazepine Dexamethasone Ethosuximide Glucocorticoids Griseofulvin Nafcillin Nelfinavir Nevirapine Oxcarbazepine Phenobarbital Phenylbutazone	Phenytoin Primidone Progesterone Rifabutin Rifampin Rofecoxib (mild) St John's wort Sulfadimidine Sulfinpyrazone Troglitazone
Inhibitors	
Amiodarone Anastrozole Azithromycin Cannabinoids Cimetidine Clarithromycin Clotrimazole Cyclosporine Danazol Delavirdine Dexamethasone Diethyldithiocarbamate Diltiazem Dirithromycin Disulfiram Entacapone (high dose) Erythromycin Ethinyl estradiol Fluconazole (weak) Fluoxetine Fluvoxamine Gestodene Grapefruit juice Indinavir Isoniazid Itraconazole	Ketoconazole Metronidazole Mibepradil Miconazole (moderate) Nefazodone Nelfinavir Nevirapine Norfloxacin Norfluoxetine Omeprazole (weak) Oxiconazole Paroxetine (weak) Propoxyphene Quinidine Quinine Quinupristin and dalfopristin Ranitidine Ritonavir Saquinavir Sertindole Sertraline Troglitazone Troleandomycin Valproic acid (weak) Verapamil Zafirlukast Zileuton

(Adapted from Cytochrome P-450 Enzymes and Drug metabolism. In : Lacy CF, Armstrong LL, Goldman MP, Lance LL eds. Drug Information Handbook 8th ed. Hudson, OH; LexiComp Inc. 2000: 1364-1371
